Table 4 Dose modification and toxicity management guidelines for immune-related AEs associated with pembrolizumab and IO combination partners

General instructions:
 
 1. Severe and life-threatening irAEs should be treated with IV corticosteroids followed by oral steroids. Other immunosuppressive treatment should begin if the irAEs are not controlled by corticosteroids. 2. All IO treatments must be permanently discontinued if the irAE does not resolve or the corticosteroid dose is not ≤ 10 mg/day within 12 weeks of the last study intervention treatment. 3. The corticosteroid taper should begin when the irAE is \leq Grade 1 and continue at least 4 weeks. 4. If IO treatments have been withheld, study intervention may resume after the irAE decreased to \leq Grade 1 after corticosteroid taper. 				
irAEs	Toxicity Grade (CTCAE v5.0)	Action With Pembrolizumab + all IO Drugs	Corticosteroid and/or Other Therapies	Monitoring and Follow-up
Pneumonitis	Grade 2	Withhold	
 • Administer corticosteroids (initial dose of 1 to 2 mg/kg prednisone or equivalent) followed by taper • Add prophylactic antibiotics for opportunistic infections 	
 • Monitor participants for signs and symptoms of pneumonitis • Evaluate participants with suspected pneumonitis with radiographic imaging and initiate corticosteroid treatment
	Recurrent Grade 2, Grade 3 or 4	Permanently discontinue		
Diarrhea/Colitis	Grade 2 or 3	Withhold	
 • Administer corticosteroids (initial dose of 1 to 2 mg/kg prednisone or equivalent) followed by taper 	
 • Monitor participants for signs and symptoms of enterocolitis (ie, diarrhea, abdominal pain, blood or mucus in stool with or without fever) and of bowel perforation (ie, peritoneal signs and ileus) • Participants with \geqGrade 2 diarrhea suspecting colitis should consider GI consultation and performing endoscopy to rule out colitis • Participants with diarrhea/colitis should be advised to drink liberal quantities of clear fluids. If sufficient oral fluid intake is not
	Recurrent Grade 3 or Grade 4	Permanently discontinue		

irAEs	Toxicity Grade (CTCAE v5.0)	Action With Pembrolizumab + all IO Drugs	Corticosteroid and/or Other Therapies	Monitoring and Follow-up
				feasible, fluid and electrolytes should be substituted via IV infusion

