AST or ALT Elevation or Increased Bilirubin	Grade 2 ^a	Withhold	
 Administer corticosteroids (initial dose of 0.5 to 1 mg/kg prednisone or equivalent) followed by taper 	
 Monitor with liver function tests (consider weekly or more frequently until liver enzyme value returned to baseline or is stable)
	Grade 3 ^b or 4 ^c	Permanently discontinue	
 Administer corticosteroids (initial dose of 1 to 2 mg/kg prednisone or equivalent) followed by taper 	
T1DM or Hyperglycemia	New onset T1DM or Grade 3 or 4 hyperglycemia associated with evidence of β -cell failure	Withhold ^d	
 Initiate insulin replacement therapy for participants with T1DM Administer antihyperglycemic in participants with hyperglycemia 	
 Monitor participants for hyperglycemia or other signs and symptoms of diabetes
Hypophysitis	Grade 2	Withhold	
 Administer corticosteroids and initiate hormonal replacements as clinically indicated 	
 Monitor for signs and symptoms of hypophysitis (including hypopituitarism and adrenal insufficiency)
	Grade 3 or 4	Withhold or permanently discontinue ^d		
Hyperthyroidism	Grade 2	Continue	
 Treat with nonselective beta-blockers (eg, propranolol) or thionamides as appropriate 	
 Monitor for signs and symptoms of thyroid disorders
	Grade 3 or 4	Withhold or permanently discontinue ^d		

irAEs	Toxicity Grade (CTCAE v5.0)	Action With Pembrolizumab + all IO Drugs	Corticosteroid and/or Other Therapies	Monitoring and Follow-up
Hypothyroidism	Grade 2, 3 or 4	Continue	
 Initiate thyroid replacement hormones (eg, levothyroxine or liothyronine) per standard of care 	
 Monitor for signs and symptoms of thyroid disorders
Nephritis: grading according to increased creatinine or acute kidney injury	Grade 2	Withhold	
 Administer corticosteroids (prednisone 1 to 2 mg/kg or equivalent) followed by taper 	
 Monitor changes of renal function
	Grade 3 or 4	Permanently discontinue		

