Neurological Toxicities	Grade 2	Withhold	
 Based on severity of AE administer corticosteroids 	
 Ensure adequate evaluation to confirm etiology and/or exclude other causes
	Grade 3 or 4	Permanently discontinue		
Myocarditis	Asymptomatic cardiac enzyme elevation with clinical suspicion of myocarditis (previously CTCAE v4.0 Grade 1)	Withhold	
 Based on severity of AE administer corticosteroids 	
 Ensure adequate evaluation to confirm etiology and/or exclude other causes
	Grade 2, 3 or 4	Permanently discontinue		
Exfoliative Dermatologic Conditions	Suspected SJS, TEN, or DRESS	Withhold	
 Based on severity of AE administer corticosteroids 	
 Ensure adequate evaluation to confirm etiology or exclude other causes
	Confirmed SJS, TEN, or DRESS	Permanently discontinue		
All Other irAEs	Persistent Grade 2	Withhold		

irAEs	Toxicity Grade (CTCAE v5.0)	Action With Pembrolizumab + all IO Drugs	Corticosteroid and/or Other Therapies	Monitoring and Follow-up
	Grade 3	Withhold or discontinue based on the event ^e	
Based on severity of AE administer corticosteroids	
Ensure adequate evaluation to confirm etiology or exclude other causes
	Recurrent Grade 3 or Grade 4	Permanently discontinue		

AE(s)=adverse event(s); ALT= alanine aminotransferase; AST=aspartate aminotransferase; CTCAE=Common Terminology Criteria for Adverse Events; DRESS=Drug Rash with Eosinophilia and Systemic Symptom; GI=gastrointestinal; IO=immuno-oncology; ir=immune related; IV=intravenous; SJS=Stevens-Johnson Syndrome; T1DM=type 1 diabetes mellitus; TEN=Toxic Epidermal Necrolysis; ULN=upper limit of normal.

Note: Non-irAE will be managed as appropriate, following clinical practice recommendations.

^a AST/ALT: >3.0 to 5.0 x ULN if baseline normal; >3.0 to 5.0 x baseline, if baseline abnormal; bilirubin:>1.5 to 3.0 x ULN if baseline normal; >1.5 to 3.0 x baseline if baseline abnormal

^b AST/ALT: >5.0 to 20.0 x ULN, if baseline normal; >5.0 to 20.0 x baseline, if baseline abnormal; bilirubin:>3.0 to 10.0 x ULN if baseline normal; >3.0 to 10.0 x baseline if baseline abnormal

^c AST/ALT: >20.0 x ULN, if baseline normal; >20.0 x baseline, if baseline abnormal; bilirubin: >10.0 x ULN if baseline normal; >10.0 x baseline if baseline abnormal

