5.8 Dose Limiting Toxicity (DLT) Monitoring

Dose Limiting Toxicity will be continuously monitored and is explicitly intended for the purposes of safety monitoring of the concurrent combination of ISA101b, pembrolizumab and cisplatin-IMRT. As defined, excess DLT is not expected during standard of care cisplatin-IMRT. Excess DLT which delays SOC CRT greater than 2 weeks, however, would trigger protocol suspension and determination of causality attribution and whether the

protocol can proceed with all or only one of the investigational agent(s). Please see Section 10.3 for details of the Continuous Monitoring Plan.

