5.8.1 DLT

DLT is defined as the occurrence of a severe adverse event (AE) listed below that is *at least possibly* related to ISA101b and pembrolizumab and occurs within 24 weeks of the initiation of ISA101b or pembrolizumab and leads to at least a two week delay in CRT. AEs will be graded according to NCI CTCAE version 5.0. The Data Safety and Monitoring Committee of the H&N Program at UPMC Hillman Cancer Center (HCC) will determine causality and whether to remove the suspension and permit the trial to proceed, in consultation with the Principal Investigator, key co-Investigator(s), ISA and Merck.

DLT Definition:

Since autoimmune/inflammatory events may occur at any time during the course of treatment, and may occur with evidence of clinical benefit, the following criteria will be used to define DLT:

- Any \geq Grade 3 non-hematologic toxicity **except**:
 - Grade 3 in-field radiation dermatitis for which IMRT is held \leq 1 week (5 fractions)
 - Grade 3 mucositis for which IMRT is held \leq 1 week (5 fractions)
 - Asymptomatic Grade 3 hypomagnesemia or hypokalemia, which corrects to Grade \leq 2 with replacement therapy
 - Grade 3 dysphagia
 - Grade 3 pain
 - Grade 3 weight loss
 - Grade 3 fatigue
- An alanine or aspartate amino transaminase elevation of greater than three times the upper limit of normal with concurrent elevation of bilirubin two times the upper limit of normal attributable to pembrolizumab should be considered a DLT. Patients meeting this criterion should be permanently discontinued from pembrolizumab.
- Autoimmune toxicity of any grade requiring systemic corticosteroids or other anti-inflammatory that cannot be tapered off in less than 12 weeks.
- Delay in completion of radiation therapy >10 fractions, or inability to complete prescribed IMRT course, due to immune toxicity at least possibly attributed to pembrolizumab or ISA101b.
- Grade \geq 3 neutropenia with fever (oral temperature $> 39^{\circ}\text{C}$)
- Grade \geq 3 thrombocytopenia with bleeding
- Grade \geq 3 local injection site reaction at the site of ISA101b injection
- Grade \geq 3 systemic allergic following ISA101b injection

Patients who experience a DLT to pembrolizumab will receive no additional doses of pembrolizumab and will be withdrawn from the protocol. Patients who experience a DLT to ISA101b will receive no additional doses of ISA101b but may continue on protocol treatment (cisplatin, IMRT, Pembrolizumab) with PI approval.

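### For one band of combined transaminase and bilirubin elevation, section 5.8.1 stops pembrolizumab permanently while Table 4 withholds it and permits resumption; neither cites the other

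*Combined protocol and SAP*

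**What the plan says.** Section 5.8.1 lists a laboratory criterion among the dose-limiting toxicities: ALT or AST above three times ULN with concurrent bilirubin of two times ULN, attributable to pembrolizumab. It adds an action: "Patients meeting this criterion should be permanently discontinued from pembrolizumab".

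The lead-in to 5.8.1 limits a DLT to an event that "occurs within 24 weeks of the initiation of ISA101b or pembrolizumab and leads to at least a two week delay in CRT". Section 5.8 says that DLT monitoring is "explicitly intended for the purposes of safety monitoring of the concurrent combination of ISA101b, pembrolizumab and cisplatin-IMRT". The closing paragraph of 5.8.1 sets a general consequence: "Patients who experience a DLT to pembrolizumab will receive no additional doses of pembrolizumab".

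Section 5.4.1 gives the dosing rules in Table 4, which apply when the investigator judges the event related to pembrolizumab. The row "AST or ALT Elevation or Increased Bilirubin" has two actions: withhold at Grade 2, and permanently discontinue at Grade 3 or 4. Footnote a defines Grade 2 as "AST/ALT: >3.0 to 5.0 x ULN if baseline normal; >3.0 to 5.0 x baseline, if baseline abnormal" for the transaminases and ">1.5 to 3.0 x ULN if baseline normal; >1.5 to 3.0 x baseline if baseline abnormal" for bilirubin. General instruction 4 begins "If IO treatments have been withheld, study intervention may resume after the irAE decreased to" and sets the level at Grade 1 or less after corticosteroid taper. General instruction 3 makes that taper at least 4 weeks. Section 5.4.1 also says that a subject who meets retreatment criteria receives the full 200 mg dose.

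**The concern.** Both rules address the same patients, those with liver test elevations attributed to pembrolizumab, but over part of the range they prescribe different actions. Table 4 has no entry for transaminases and bilirubin rising together. Section 5.4.1 and Table 4 do not mention 5.8.1, and 5.8.1 mentions neither of them.

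Table 4 is the natural reference when deciding on the next infusion. A site that consults it alone would see a Grade 2 event, hold the drug, treat with steroids, taper, and find that resumption is allowed. Nothing there says that section 5.8.1 bars a further dose. What is at stake is re-exposure after a liver event for which the protocol itself prescribes a permanent stop.

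**Working it through.** No sample size, power or error rate is involved, and the plan states no figure to reproduce. The check intersects the two sets of thresholds.

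**Inputs, normal baseline, in multiples of ULN**

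| Source | AST or ALT | Bilirubin | Action |
|---|---|---|---|
| 5.8.1 laboratory criterion | >3, no upper limit | 2, read as at least 2 | Permanent stop |
| Table 4, Grade 2 (footnote a) | >3 to 5 | >1.5 to 3 | Withhold; may resume |
| Table 4, Grade 3 or 4 (footnotes b, c) | >5 | >3 | Permanent stop |

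Section 5.8.1 gives no inequality sign for bilirubin. At least 2x is the natural reading, and even exactly 2x lies inside the Grade 2 range.

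**Intersection.** AST/ALT: (>3) and (>3 to 5) gives >3 to 5. Bilirubin: (at least 2) and (>1.5 to 3) gives 2 to 3. The actions differ for AST/ALT >3 to 5x ULN with bilirubin 2 to 3x ULN. Above 5x for the transaminases or 3x for bilirubin, both sections stop the drug.

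**Examples.**
- ALT 4x with bilirubin 2.5x: 5.8.1 stops permanently; Table 4 withholds and allows resumption.
- ALT 4x with bilirubin 1.7x: 5.8.1 is not met, so there is no difference.
- ALT 6x with bilirubin 2.5x: both stop.

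**What the liver bullet adds.** The first DLT bullet in 5.8.1 already covers non-hematologic toxicity of Grade 3 or higher and lists no liver exception. With a normal baseline, anything above 5x or 3x is Grade 3 or higher. What the liver bullet adds to the DLT list is therefore the band below Grade 3, which is exactly where Table 4 only withholds.

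**Abnormal baseline.** Table 4 rescales to baseline and 5.8.1 does not. Section 3.1, Table 1 admits AST/ALT up to 2.5x ULN. The Grade 2 range for AST/ALT then becomes:
- baseline 1.5x: 3 x 1.5 = 4.5x to 5 x 1.5 = 7.5x ULN;
- baseline 2.5x: 3 x 2.5 = 7.5x to 5 x 2.5 = 12.5x ULN.

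The 5.8.1 limit stays at 3x ULN, so the mismatch can be wider for these patients if the rise is attributed to pembrolizumab. Table 1 also admits total bilirubin above 1.5x ULN when direct bilirubin is within ULN, and 5.8.1 does not say how its bilirubin limit applies to them.

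**Scope of the stop.** If the lead-in governs the bullet, only events within 24 weeks that delay chemoradiotherapy by at least two weeks count, and an event after chemoradiotherapy has ended could not qualify. If the stop sentence is read alone, its criterion is the laboratory one and has no time limit.

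**The case against.** The strongest reply is that the sections do not collide. The Table 4 row is general, 5.8.1 is specific to the combined pattern, and instruction 4 only permits resumption. A site that follows both does not resume. That stands: a reader might infer that compliance with both is impossible, and the documents do not support that. Reading the specific rule as controlling is sensible, but the protocol does not state it, and the full-dose sentence in 5.4.1 points the other way for a site using only that section.

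A second reply is that safeguards would catch the case. Section 12.4.2 requires a near-identical pattern to be reported to the Sponsor within 24 hours, and serious events are reported under 12.4.1. Table 14 requires the Principal Investigator's advance approval of re-challenge if the event was serious and possibly caused by pembrolizumab, or if re-exposure carries additional significant risk; the second limb could cover a non-serious event. Section 5.7 lets the Sponsor stop treatment, section 13 provides monthly review, and the taper leaves weeks for these to work. All of this lowers the risk. It does not remove it: the 12.4.2 pattern also requires alkaline phosphatase below 2x ULN and concerns reporting and evaluation rather than dosing, and the Table 14 approval refers back to the dose modification guidelines.

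A reader might also infer that Table 4 is the sole liver rule once chemoradiotherapy is over. That is not established. Section 5.4.1 refers to treatment guidance in a separate guidance document for events of clinical interest, which is not in the file.

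Nor do the documents show that the 5.8.1 stop runs throughout treatment. The closing paragraph already ends pembrolizumab after any DLT to it, so a stop sentence confined to DLTs would be redundant. But this protocol often repeats itself (the 17-dose statement appears in sections 5, 5.1.2, 5.3.3 and 5.6), and the bullet sits in a DLT definition tied to the concurrent phase. The scope is ambiguous.

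**Conclusion.** The inconsistency is real and limited. With a normal baseline it covers pembrolizumab-attributable AST/ALT above 3 to 5x ULN with concurrent bilirubin 2 to 3x ULN, reading the 5.8.1 bilirubin limit as at least 2x. Under the broader reading this applies whenever pembrolizumab is being given; under the narrower reading, only to events that also meet the DLT lead-in. The difference in actions exists under either.

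The consequence is a possible re-dose, by a site working from Table 4, of a patient whom 5.8.1 stops. The event is assumed to be rare; the documents give no frequency, so no count of affected patients is offered. The two sections govern dosing, not the endpoint, sample size or test, so the progression-free survival analysis is unaffected. Confidence is high in the overlap and lower in how often it would matter. It should be fixed because the correction is cheap and protects patients.

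**What to change.** Add a footnote to the AST/ALT/bilirubin row of Table 4: AST/ALT above 3x ULN with concurrent bilirubin at or above 2x ULN, attributable to pembrolizumab, means permanent discontinuation of pembrolizumab, per 5.8.1.

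In 5.8.1, state whether the stop applies throughout pembrolizumab treatment or only to events meeting the DLT lead-in. The first is the safer choice and fits the plain wording of the stop sentence, but the decision is the sponsor's; if the narrower scope is chosen, the footnote should carry the same limit. State also how the rule applies with abnormal baseline values, including patients enrolled with total bilirubin above 1.5x ULN and direct bilirubin within ULN.

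The cost is one decision on scope and a few lines of text. No visits or tests are added: liver panels are already scheduled weekly from week -2 to week 7 (10 panels) and every 3 weeks from week 8 to week 47 ((47 - 8)/3 + 1 = 14 panels), 24 in all. The downside is that a few patients who could have resumed under Table 4 will stop.

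As a separate clerical correction, section 5.7 points to 5.2.4 (order of ISA101b administration) for dose modification; it should point to 5.4. That alone would not close the gap, because it leads to Table 4 as it now stands.

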6. RESPONSE ASSESSMENT

Patients will undergo clinical neck and chest exam and CT scan with IV contrast at baseline and at 12-14 weeks following completion of IMRT. Note, an integrated PET/CT with contrasted diagnostic CT scan is recommended if

feasible at the participating site; however, only a diagnostic CT scan is required. Rare patients may require an MRI for tumor measurements, due to allergy to iodinated contrast despite premedication. In these patients, MRI of the neck should be performed at baseline and at first response assessment.

Responses will be coded for:

- Clinical examination response, primary and nodes
- CT response, primary and nodes (see modified RECIST criteria version 1.1, Section 6.1)
- If applicable: Integrated PET/CT response, primary and nodes (see Integrated PET/CT response criteria, Section 6.2.4)

6.1 Solid Tumor Response Criteria (modified RECIST Criteria version 1.1)

6.1.1 Malignant Disease Evaluation

To assess objective response, it is necessary to estimate the overall tumor burden at baseline to which subsequent measurements will be compared. Measurable disease is defined by the presence of at least one measurable lesion.

All measurements should be recorded in metric notation by use of a ruler or calipers. The same method of assessment and the same technique should be used to characterize each identified lesion at baseline and during follow-up. All baseline evaluations should be performed as closely as possible to the beginning of treatment and never more than four weeks before treatment registration.

The term unevaluable in reference to measurability will not be used because it does not provide additional meaning or accuracy.

At baseline, the primary tumor and pathologic neck lymph nodes will be characterized as either measurable or non-measurable.

6.1.1.1 Measurable Disease

6.1.1.1.1 Primary Tumor

Lesions that can be accurately measured in at least one dimension (longest diameter to be recorded) as ≥ 20 mm (2.0 cm) using conventional techniques or as ≥ 10 mm (10 cm) using spiral CT scan.

6.1.1.1.2 Neck lymph nodes

- Neck lymph nodes are considered pathologic and measurable if short axis ≥ 15 mm.
- Neck lymph nodes are considered pathologic but non-measurable if short axis ≥ 10 mm but < 15 mm.
- Neck lymph nodes are considered non-pathologic and non-measurable if short axis < 10 mm.

6.1.1.2 Non-measurable Disease

- All other lesions, including small lesions [longest diameter < 20 mm (2.0 cm) with conventional techniques or < 10 mm (1.0 cm) with spiral CT scan] are truly non-measurable lesions.
- Lesions considered to be truly non-measurable include the following: bone lesions, leptomeningeal disease, ascites, pleural/pericardial effusion, inflammatory breast disease, lymphangitis cutis/pulmonis, abdominal masses that are not confirmed and followed by imaging techniques, and cystic lesions.

6.1.2 Definition of a Response

6.1.2.1 Target Lesions

All measurable lesions, including the primary tumor, and up to a maximum of five neck lymph nodes, should be measured at baseline.

The sum of the longest diameter of the primary tumor, and the short axis diameter of target pathologic lymph nodes, will be calculated at baseline and reported as the *baseline sum diameter*.

6.1.2.1.1 Complete Response (CR)

The disappearance of the primary tumor and the resolution of pathologic neck adenopathy. For the definition of

radiographic complete response in the neck, the resolution of neck lymph nodes to < 10 mm in short axis diameter with non-pathologic appearance is sufficient.

6.1.2.1.2 Partial Response (PR)

At least a 30% decrease in the sum of target lesion diameters (longest diameter of the primary tumor; short axis diameter of the target lymph nodes), taking as reference the *baseline sum diameter*.

6.1.2.1.3 Progressive Disease (PD)

At least a 20% increase in the sum of target lesion diameters (longest diameter of the primary tumor; short axis diameter of the target lymph nodes), taking as reference the *smallest sum diameter* recorded since the baseline sum diameter measurements, or the appearance of one or more new lesion(s).

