5.7 Participant Discontinuation Criteria

Discontinuation of study intervention does not represent withdrawal from the study.

As certain data on clinical events beyond study intervention discontinuation may be important to the study, they must be collected through the participant's last scheduled follow-up, even if the participant has discontinued study intervention. Therefore, all participants who discontinue study intervention prior to completion of the protocol-specified treatment period will still continue to be monitored in this study and participate in the study visits and procedures as specified in Section 2.2 unless the participant has withdrawn from the study.

Participants may discontinue study intervention at any time for any reason or be discontinued from the study intervention at the discretion of the investigator should any untoward effect occur. In addition, a participant may be discontinued from study intervention by the investigator or the Sponsor if study intervention is inappropriate, the study plan is violated, or for administrative and/or other safety reasons.

A participant must be discontinued from study treatment but continue to be monitored in the study for any of the following reasons:

- The participant or participant's legally acceptable representative requests to discontinue study intervention
- After prolonged study intervention interruption that prohibits restarting study intervention if agreed upon with the Sponsor
- Radiographic disease progression [outlined in Section 6.1.4](#).
- [Any progression or recurrence of malignancy, or any occurrence of another malignancy that requires active treatment](#)
- Any study intervention-related toxicity specified as a reason for permanent discontinuation as defined in the guidelines for dose modification due to AEs in Section 5.2.4.
- The participant has a medical condition or personal circumstance which, in the opinion of the investigator and/or sponsor, placed the participant at unnecessary risk from continued administration of study treatment.
- The participant has a confirmed positive serum pregnancy test

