6.1.3.2 Confirmation of Response

To be assigned a status of complete or partial response, changes in tumor measurements must be confirmed by repeat assessments performed no less than four weeks after the criteria for response are first met.

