6.2.1 CT and MRI

CT and magnetic resonance imaging (MRI) are the best currently available and most reproducible methods for measuring target lesions. Conventional CT and MRI should be performed with contiguous cuts of 10 mm or less in slice thickness. Spiral CT should be performed by use of a 5 mm contiguous reconstruction algorithm. This specification applies to tumors of the chest, abdomen, and pelvis, while head and neck tumors, and those of the extremities require specific procedures.

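### Progression has no minimum size, so one scan can meet both complete response and progression, and the plan does not say which counts for PFS

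*Combined protocol and SAP*

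**What the plan says.** - **Progression (6.1.2.1.3).** Target-lesion progression is "At least a 20% increase in the sum of target lesion diameters", measured against the smallest sum since baseline; a new lesion also counts. Section 6 contains no absolute minimum increase and no minimum node size.
- **The sum (6.1.2.1).** It adds the longest diameter of the primary to the short axes of the target nodes: "up to a maximum of five neck lymph nodes, should be measured at baseline". Nothing says how a resolved node enters the sum.
- **Complete response (6.1.2.1.1; 6.3 is similar).** In the neck, "the resolution of neck lymph nodes to < 10 mm in short axis diameter with non-pathologic appearance is sufficient". A complete responder can therefore carry a non-zero sum.
- **Node status (6.1.1.1.2).** "Neck lymph nodes are considered non-pathologic and non-measurable if short axis < 10 mm".
- **Confirmation (6.1.3.2).** "To be assigned a status of complete or partial response, changes in tumor measurements must be confirmed by repeat assessments". No confirmation is asked for progression.
- **Use.** Progression is a PFS event (6.1.3.7), and PFS drives the primary test (10.4) and the futility rule (10.5). Section 5.7 lists radiographic progression under "A participant must be discontinued from study treatment but continue to be monitored in the study for any of the following reasons" and points to a Section 6.1.4 that does not exist.
- **Named standard.** Section 8.3.1.1 and footnote g of Appendix C call for RECIST 1.1. Section 6.1 is headed as a modified version and writes out its own rule.

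**The concern.** After successful chemoradiation the primary may contribute 0 mm and the nodes a few millimetres each. A 20% rise on such a sum can be 1 to 3 mm. The reference is the lowest reading so far, so a single low reading makes the next ordinary one look like growth.

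A stable responder could then be scored as a PFS event. The 65% null in 10.2 is built in part on a 3-year overall survival figure, which this rule cannot affect, so false progressions push one way: against the regimen. They would reduce power and enter the futility calculation in 10.5. If sites instead set the rule aside by judgement, investigators in an open-label single-arm trial, with no central review described, would decide case by case which increases count.

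**Working it through.** **1. The two definitions on one scan.** Take a patient with the primary gone and one residual target node.
- Node 6 mm, later 8 mm: (8 - 6)/6 = 33%, at least 20%, so progression under 6.1.2.1.3.
- The same 8 mm node is under 10 mm, so non-pathologic under 6.1.1.1.2. With a normal appearance the patient still meets complete response under 6.1.2.1.1 and 6.3.
- Table 9 has rows for target CR and for target PD, but nothing for when both hold.

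**2. When this can happen.** A 2 mm change reaches 20% only if 2/nadir is at least 0.20, that is, a nadir sum of 10 mm or less. With two 6 mm nodes, 2/12 = 16.7%; with three, 2/18 = 11.1%; with five, 2/30 = 6.7%. None of these is progression. Larger sums need a larger combined change. If resolved nodes were recorded as 0, the example would disappear, but a 20% rise on a zero sum is undefined.

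**3. The plan's power.** Inputs from 10.2: N = 45, one-sided alpha 0.10, 2-year PFS 65% against 81%, 2 years of accrual and 1 of follow-up.
- Hazard = -ln(S)/2: 0.2154 under the null, 0.1054 under the alternative.
- With uniform accrual, P(event) = 1 - (e^(-h) - e^(-3h))/(2h), giving 15.5 and 8.5 expected events.
- Critical hazard = 0.2154 x (1 - 1.2816/sqrt(15.5)) = 0.1453.
- Power = Phi[(0.1453 - 0.1054)/(0.1054/sqrt(8.5))] = 86.5%, matching the stated 87%.

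**4. Power with false events.** Let an assumed share f of patients have a false event by 2 years, independent of true events, so observed 2-year PFS = 0.81 x (1 - f). The formula column treats this as exponential. The simulation places false events at scan times.

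| f (assumed) | 2-year PFS | Power, formula | Power, simulation |
|---|---|---|---|
| 0 | 81.0% | 86.5% | 85% |
| 2% | 79.4% | 78% | 80% |
| 5% | 77.0% | 64% | 69% |
| 10% | 72.9% | 39% | 50% |

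At f = 10% the loss is 81 - 72.9 = 8.1 points of the 16-point effect, about half.

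**5. Chance of a false progression for one stable patient.** Six scans to 24 months (the 12-14 week scan, then 6, 9, 12, 18 and 24 months), readings rounded to 1 mm, running nadir, and normal reading error with an assumed SD of 0.5 or 1.0 mm per node. The documents give no reading error.

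| Stable nodes of 7 mm | SD 0.5 mm | SD 1.0 mm |
|---|---|---|
| one | 25% | 75% |
| two | 13% | 65% |
| three | 6% | 53% |
| five | 0.2-0.3% | 24% |

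Requiring both a 5 mm absolute rise (an assumed value) and a node of 10 mm or more reduces the first three rows to 0% at SD 0.5, and to 0.6%, 2.5% and 4.4% at SD 1.0. The two conditions do different work. For one 8 mm node at SD 1.0, 74% falls to 27% with the 10 mm condition alone and to about 1% with the 5 mm floor alone.

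**The case against.** The strongest reply is that RECIST 1.1 is required by 8.3.1.1 and Appendix C, so 6.1.2.1.3 is only a summary. Whether that standard supplies a floor cannot be settled from the documents, and they do not say it overrides a rule written out under a modified heading. That leaves two candidate rules rather than an answer.

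Other text leans against the literal reading. Section 6.2.4 says that a short axis under 1 cm no longer counts as residual disease. Section 6.1.3.4 ends complete response at objectively documented recurrence, and 8.3.1.2 and 8.3.3 provide for specialist evaluation and biopsy. This stands: the documents show an unresolved precedence. A reader might infer that every 6-to-8 mm node will be called progressed, but that does not follow.

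Three further inferences are tempting and unsupported:
- **That such changes are below scanner resolution.** Section 6.2.1 says "Spiral CT should be performed by use of a 5 mm contiguous reconstruction algorithm", but its next sentence confines this to chest, abdomen and pelvis and leaves head and neck tumors to specific procedures.
- **That many patients would lose treatment.** Dosing ends at week 47. Of the scans that could follow a post-treatment nadir, only those at 6 and 9 months, near weeks 33 and 46, fall within dosing; five doses and one dose then remain. Restricted to these, one 7 mm node gives 7% / 35%.
- **That false-positive error is inflated.** The bias runs against the regimen.

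It also stands that the share of patients with small residual nodes is nowhere given, so the per-patient chances do not yield a trial-wide rate.

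**Conclusion.** The concern holds as a defect in how the primary endpoint is defined. On a small nadir sum (10 mm or less for a 2 mm change), a patient can be in complete response and in progression at once, and neither Table 9 nor the references to RECIST 1.1 say which applies. Followed literally, the rule turns reading variation in responders into PFS events.

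The size is conditional. The chances of 25% / 75% for one 7 mm node, down to under 1% / 24% for five, rest on an assumed reading error and on nodes that are truly stable. Power of 64-69% rests on an assumed 5% false-event rate. The stated 87% is not wrong; it presumes no false events. A reader might conclude that a 10% false-event rate would consume most of the planned effect. Under independence it costs about half, though power then falls to 39-50%. With the frequency unknown, this is a clarification to settle before PFS is analysed, not a demonstrated failure of the trial.

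**What to change.** For scoring the PFS endpoint, amend 6.1.2.1.3 and Table 9 so that:
1. A patient who still meets the complete response definition (primary absent, all nodes under 10 mm short axis and non-pathologic in appearance, no new lesion) is not progressed on target lesions.
2. A nodal increase counts only if at least one target node is 10 mm or more, the cut-off in 6.1.1.1.2.
3. The sum must also rise by an absolute minimum, chosen and justified by the sponsor. The 5 mm used above is an assumption with no source in the documents.

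The new-lesion criterion stays as it is. State whether 6.1 or RECIST 1.1 governs, and reconcile 5.7 (including its reference to Section 6.1.4), 6.1.2.1.3, 8.3.1.1 and Appendix C. Section 5.7 ties progression to discontinuation, so the sponsor must settle how the endpoint wording and that section fit together; no treatment-stopping rule is proposed here.

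The cost is a few sentences and a change to the response form, with no extra imaging. There are two downsides. True regrowth below 10 mm would be dated at the next scan, 3 to 12 months later on the 8.4 schedule. Protection is also limited when several nodes sit near 10 mm: for three 8 mm nodes at SD 1.0, the chance of a false progression falls only from 33% to 23%.
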